## 2.1 Primary Objective (or Aim)

The primary objective of this study is to determine the effectiveness of the *OPTI-VENT* bundle to improve survival to discharge with favorable neurological outcome among children receiving at least 1 minute of CPR.

In embedded observational studies, the secondary objectives are to:

- Determine if there is an alternative ventilation rate that is associated with improved 1) survival outcomes and 2) intra-arrest physiology (e.g., blood pressure).
- Determine the association between Airway Opening Index and 1) survival outcomes and 2) intra-arrest physiology (e.g., blood pressure and exhaled carbon dioxide)
- Determine if AOI can be modified by changing airway pressures delivered during CPR using novel multidimensional machine learning algorithms.

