#### 4 STUDY PROCEDURES

Standard cardiac arrest data (e.g., demographics, intra- and post-arrest physiologic variables, CPR quality variables) will be collected on all subjects, extracted from the electronic medical record, continuous bedside monitors, and other patient physiologic monitoring devices (e.g., NIRS). Data elements to be collected from the pre-, intra-, and post-arrest periods include but are not limited to:

Patient Characteristics: date of birth; sex; race/ethnicity; height; weight; illness category (medical cardiac, medical non-cardiac, surgical cardiac, surgical non-cardiac, trauma). Pre-existing conditions: respiratory insufficiency; hypotension; congestive heart failure; pneumonia; sepsis; trauma; renal insufficiency; malignancy; congenital heart disease, if yes, single ventricle; if single ventricle, the anatomy is specified; if surgical palliation completed, type of most recent surgical procedure is noted (Norwood with Sano modification, Norwood with modified BT shunt, Hybrid Procedure, Bi-directional Glenn, Fontan, other); vasoactive inotropic scores (2 hours preceding CPR); pediatric cerebral performance category (PCPC) score; functional status scale (FSS) score.

CPR Event Characteristics: interventions at CPR start (e.g., vasoactive infusion); immediate cause of arrest (Y/N for hypotension, respiratory decompensation, arrhythmia, cyanosis without respiratory decompensation); first documented rhythm requiring CPR; time of first shockable rhythm; pre-shock pause (seconds); time of first defibrillation; time of first vasopressor administration for non-shockable rhythm; drug interventions during CPR; duration of CPR (minutes). CPR mechanics variables: Compression depth (mm); rate (per minute); chest compression fraction; and leaning during relaxation phase (release velocity, if available [mm/second]). Ventilation variables: ETCO2 (mmHg); ventilation rate (bpm); airway opening index; other ventilation variables as available (e.g., Peak Inspiratory Pressure [cmH2O]). Intra-arrest physiology (arterial BP (mmHg), ETCO2 (mmHg), and arterial/venous blood gases.

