#### Primary Objective (Efficacy of OPTI-VENT bundle)

The analysis of our primary outcome is based on all enrolled index events (first in-ICU cardiac arrest) excluding transition periods. For the primary analysis of the interventional trial, a mixed effect logistic regression model will be fit with our primary outcome as the dependent variable. The primary predictor will be treatment group, an indicator of whether the *OPTI-VENT* bundle was fully implemented prior to the arrest. Fixed covariates will be illness category, age, first documented rhythm, and time since trial start (to prevent confounding due to unrelated temporal changes in outcome). Etiology and severity of pre-existing lung disease will be evaluated as a confounder / effect modifier. Unit will be included as a random effect to account for heterogeneity in patient outcomes across ICUs and to accommodate clustering of patients within ICUs. The null hypothesis will be tested using the standard type III test for the fixed effect, and the p-value for the two-sided alternative will be presented.

Brief Description of Secondary Analytic Objectives

Ventilation Rate and Survival: We will explore the relationship between ventilation rate and survival using cubic splines and ROC curves. We will randomly divide our cohort into a derivation set (70%) and a validation set (30%). The derivation set will be used in an exploratory fashion to identify an optimal target using cubic splines and ROC curves in conjunction with clinical expertise. Then, the validation set will be used to validate the rate selected and to provide an unbiased estimate of the effect of achieving the target rate on outcome. Cubic splines will allow us to create a smooth curve of survival probability on the vertical axis against the event-level average ventilation rate on the horizontal axis, while controlling for potential confounders. We plan to stratify our analysis by age,

**Figure 2:** Airway Opening Index. The sum of the delta in ETCO2 divided by the max ETCO2 caused by each chest compression is averaged by the number of CCs. Higher values indicate greater airway patency.

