and either adjust for / stratify by initial rhythm, immediate cause of arrest (e.g., respiratory deterioration, shock, sudden arrhythmia), severity (none, non-severe, severe) and etiology (none, obstructive, restrictive, mixed) of pre-existing lung disease, chest compression depth and rate (AHA compliant vs. not), and clinical site. If an alternative ventilation rate target is identified, we will quantify its association with survival outcomes using logistic regression models. Similarly, we will also explore the relationship between ventilation rate and 1) arterial diastolic BP and 2) exhaled carbon dioxide using linear regression models. For this analysis, individual epoch data will be used. Models will be adjusted for the same variables as above and account for the clustering of epochs from within events.

Evaluation of Airway Opening Index: The calculation of Airway Opening Index will be done in the manner as described in Grieco et.al. (Figure 2). As with other variables, an average AOI for each 30-second CPR epoch will be calculated. For each event, the average of all the epochs will be calculated to be used in logistic regression survival analyses. Epoch-level data will be used in a similar fashion as described above to evaluate the association of AOI with intra-arrest physiology (e.g., blood pressure and ETCO2) and delivered airway pressures (e.g., positive end expiratory pressure) in linear regression models, accounting for the clustering of epochs from within events. In addition to these standard statistical methods, this exploratory aim will involve the development of a multi-modal ML model. The input data will comprise both discrete values (e.g., demographic and clinical variables, ETCO2, I/E ratio) and high-fidelity waveform data (e.g., arterial BP, capnogram). To evaluate model performance, we will use metrics such as accuracy, F1-score, and AUC-ROC.

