#### Secondary Analytic Objectives

Ventilation Rate and Survival: We conservatively estimate that ~20% of our subjects will not have usable ventilation data. Given the remaining cohort (~1200 patients), we will have more than 90% power to detect an improvement in survival from 30% to 40% if the ventilation rate is at target in 40%-60% of subjects. Given the absolute change in survival associated with the ventilation target from our preliminary data was >20%, we are conservatively powered for the primary objective of this aim. In subgroups as small as 350, we will have >80% power to detect an improvement in survival probability from 30% to 45%. Additionally, our preliminary data demonstrate that >25% of our patients with usable ventilation data will also have usable arterial BP data. With 300 subjects, we have >80% power to detect an association between ventilation rate and diastolic BP (assumptions: standard deviation of 10 mmHg for both; slope of line -2.10 mmHg / 10 bpm; ≥seven 30-second epochs of data per subject; within subject correlation of 0.60; two-sided alpha = 0.05).

Airway Opening Index: As this objective is exploratory in nature, a power calculation is not provided.

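### The physiology objective looks for a better ventilation rate, but section 6.3 names splines only for survival and leaves elapsed CPR time out of the epoch-level blood pressure and CO2 models

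*Protocol*

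**What the plan says.** Section 2.1 of the protocol lists, among the embedded observational objectives, "Determine if there is an alternative ventilation rate that is associated with improved 1) survival outcomes and 2) intra-arrest physiology", with blood pressure as the example.

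Section 6.3 treats the two halves of that objective differently.

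- **Survival:** "We will explore the relationship between ventilation rate and survival using cubic splines and ROC curves", with a 70/30 derivation and validation split.
- **Physiology:** "we will also explore the relationship between ventilation rate and 1) arterial diastolic BP and 2) exhaled carbon dioxide using linear regression models". It adds "For this analysis, individual epoch data will be used" and then "Models will be adjusted for the same variables as above and account for the clustering of epochs from within events".

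The variables referred to are age, initial rhythm, immediate cause of arrest, severity and etiology of lung disease, compression depth and rate, and site. Elapsed CPR time and vasopressor exposure are not among them.

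Section 6.4 powers the DBP analysis on 300 subjects with a "slope of line -2.10 mmHg / 10 bpm". Section 4 collects "time of first vasopressor administration for non-shockable rhythm; drug interventions during CPR", as well as CPR duration.

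**The concern.** To find a better rate, a model must be able to show that an intermediate rate beats both lower and higher ones. A straight line has no interior maximum. It names the lowest or the highest observed rate as best, or it shows no association.

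The second issue comes from using repeated 30-second epochs. Within an event, rate and DBP can both change with time. Apart from compression quality, the listed covariates are fixed within an event. A shared time trend would therefore load onto the rate coefficient.

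What is at stake is the reading of an exploratory result that may inform later rate targets. The randomized comparison is not at stake.

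**Working it through.** **1. The plan's own power figure (section 6.4).** The inputs are 300 subjects, at least 7 epochs each, SD 10 for both variables, slope -2.10 per 10 bpm, within-subject correlation 0.60 and two-sided alpha 0.05.

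- Correlation: r = 0.21 × 10 / 10 = 0.21, and atanh(0.21) = 0.2132.
- Effective n of 300 (one epoch each): 0.2132 × √297 - 1.96 = 1.71, so power is 95.7%.
- Effective n of 2100 / (1 + 6 × 0.60) = 456.5: 0.2132 × √453.5 - 1.96 = 2.58, so power is 99.5%.

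The stated power above 80% holds with room to spare, but only for a straight-line effect.

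**2. A straight line fitted to a peak.** This is an illustration; the protocol gives no curve. Let DBP = c - k(rate - 25)², 3 mmHg lower at 10 bpm from the peak, so k = 3/100 = 0.03. If rates are spread symmetrically around a mean m, the fitted slope is -2k(m - 25) per bpm, whatever their SD.

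| Mean rate (bpm) | Slope (mmHg per 10 bpm) |
|---|---|
| 20 | -0.06 × (-5) × 10 = +3.0 |
| 25 | 0 |
| 30 | -0.06 × 5 × 10 = -3.0 |

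The same curve gives three different conclusions, depending only on where the observed rates sit. A simulation used a gentler peak (2.1 mmHg lower 10 bpm away), 300 subjects, 7 epochs and within-subject correlation 0.60. With rates centred on the peak, the straight line rejected in 6% of runs. A quadratic term was detected in about 100%, with the peak recovered at 25.0 bpm.

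**3. Leaving out elapsed time.** All inputs here are assumptions: no true rate effect, rate drifting up 1 to 2 bpm per minute, a 5 to 8 mmHg step in DBP at a time uniform over minutes 1 to 5, and rate SDs of 8 between and 6 within events. Write b for the drift, d for the step, t for epoch time in minutes and p(t) for the chance that the step has happened by t.

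- Pooled slope per bpm: b·d·cov(t, p) / (8² + 6² + b²·var t).
- Within-event slope per bpm, for E epochs: b·d·cov(t, p) / (6²·(E - 1)/E + b²·var t).

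At epoch midpoints, cov(t, p) and var t are 0.201 and 1.00 for 7 epochs, and 0.759 and 4.06 for 14. For example, with b = 2, d = 8 and 7 epochs, the pooled slope is 10 × 16 × 0.201 / (100 + 4) = +0.31 mmHg per 10 bpm. The within-event slope is 10 × 16 × 0.201 / (30.9 + 4) = +0.92.

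Simulated ranges, in mmHg per 10 bpm, agree with these formulas:

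| Epochs per event | Pooled | Within event |
|---|---|---|
| 7 | about +0.1 to +0.3 | about +0.25 to +0.9 |
| 14 | about +0.4 to +1.05 | about +1.0 to +2.5 |

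The powered effect is -2.10. With no drift the bias is zero, and with downward drift its sign flips. In these simulations, adding elapsed time alone returned the slope to zero within simulation error.

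**The case against.** Four points can be made for the plan.

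- **Linear regression names a model class.** It can carry spline terms, and the sentence opens by likening itself to the survival analysis. The slope in section 6.4 is a power assumption and does not by itself fix the analysis model. This stands: a reader might infer that the protocol commits to straight lines, and the text does not go that far. Even so, splines are described only for survival and a single slope is the only form given for DBP, so the straight-line reading is the natural one and should be closed off.
- **No DBP peak is documented.** Section 1.4 describes a one-directional worry, that higher rates reduce venous return. A negative slope tests that. This also stands, and it makes the peak above an illustration. But the objective asks for a better rate, and a test of one direction does not answer that.
- **Drift is not quantified.** A reader might infer that the model will credit rate with a drug effect, or even reverse the DBP relation. The documents do not support this. Added to -2.10, the largest 7-epoch bias leaves -1.2 (-2.10 + 0.9), and the largest pooled 14-epoch bias leaves -1.05. Only the top of the 14-epoch within-event range changes the sign (-2.10 + 2.5 = +0.4).
- **Detail may sit in the SAP.** This is an exploratory secondary analysis, and functional form is often settled there. That lowers the weight of the point. It does not remove it, because the protocol itself names the method for each half of the objective and fixes the covariates by reference.

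**Conclusion.** The point holds and is minor. As written, section 6.3 gives the physiology half of the objective a method that, on its natural reading, cannot show an intermediate optimum, while the survival half gets one that can. That mismatch needs no numerical assumption. The slopes of +3.0, 0 and -3.0 rest on an assumed symmetric peak at 25 bpm.

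Leaving out elapsed time creates a risk of bias, not a demonstrated one. Its direction and size depend on how rate moves during CPR, which the protocol does not report.

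It would go too far to say that vasopressor dosing must be in the main model. Dosing may respond to low DBP, and so may lie downstream of earlier ventilation, in which case adjusting for it can add bias. First-dose time is also named only for non-shockable rhythms. The primary trial analysis and the stated DBP power are unaffected.

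**What to change.** In section 6.3:

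1. State that ventilation rate enters the epoch-level DBP and exhaled CO2 models through the same cubic splines as in the survival analysis. Read any alternative rate from that curve, and keep the straight-line slope as the powered summary.
2. Add elapsed CPR time (epoch number) to the covariates of these models.
3. Add time-varying vasopressor status (before or after first dose, where recorded) as a sensitivity analysis only, and state the limit on first-dose times.

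The cost is a few degrees of freedom and some wording. Epoch order already exists in the data, so step 2 needs nothing new. Section 6.4 should say that its DBP power figure applies to the summary slope only.

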## 6.4 Sample Size and Power

Primary Objective (Efficacy of OPTI-VENT bundle)

Based on pediRES-Q data, ~360 index CPR events are expected to occur annually. After excluding ~7 events/year that occur during transition periods, 1500 index events will be available for analysis. In our preliminary work, rates consistent with 2020 AHA Guidelines were associated with

	Compliance with Ventilation Rate Target (20 – 30 bpm)			
Absolute improvement in survival with favorable neurologic outcome	85%	90%	95%	
12%	70%	76%	82%	
14%	82%	87%	91%	
16%	91%	94%	97%	

an improvement in survival with favorable neurologic outcome of >20 percentage points. Understanding that it is likely that the magnitude of the effect will be smaller in a multicenter study, we have provided estimated power to detect a 12-16% improvement when

the target rate is achieved compared to a baseline rate of survival with favorable neurologic outcome of 30% (data obtained from an existing pediRES-Q online real-time dashboard) when the target rate is not achieved. We also show the impact of the level of compliance with the target rate that we can achieve in the intervention group compared to a control group rate of 20%. We have assumed an intra-cluster correlation of 2% (based on our prior IHCA data). To ensure adequate power, we have included a pre-planned adaptive design. If after 12 months of enrollment, sites are enrolling ≤90% of expected, we will add 6 additional ICUs. If they are enrolling ≤75% of expected, we will add an additional 10 ICUs. As the pediRES-Q network has more than 50 active domestic / international sites, recruiting 10 sites is feasible. New sites if added will all begin in the control group starting at 14 months and will randomly be assigned a transition time according to a standard stepped-wedge design. Start-up within 2 months is feasible due to these sites starting in control, our plan for continuous enrollment monitoring, and the infrastructure of the pediRES-Q network (active IRBs and DUAs). Our design adaptation can also be used to mitigate power issues due to unexpectedly high baseline compliance in the control group or inability to achieve compliance training targets in the interventional group.

#### Secondary Analytic Objectives

Ventilation Rate and Survival: We conservatively estimate that ~20% of our subjects will not have usable ventilation data. Given the remaining cohort (~1200 patients), we will have more than 90% power to detect an improvement in survival from 30% to 40% if the ventilation rate is at target in 40%-60% of subjects. Given the absolute change in survival associated with the ventilation target from our preliminary data was >20%, we are conservatively powered for the primary objective of this aim. In subgroups as small as 350, we will have >80% power to detect an improvement in survival probability from 30% to 45%. Additionally, our preliminary data demonstrate that >25% of our patients with usable ventilation data will also have usable arterial BP data. With 300 subjects, we have >80% power to detect an association between ventilation rate and diastolic BP (assumptions: standard deviation of 10 mmHg for both; slope of line -2.10 mmHg / 10 bpm; ≥seven 30-second epochs of data per subject; within subject correlation of 0.60; two-sided alpha = 0.05).

Airway Opening Index: As this objective is exploratory in nature, a power calculation is not provided.

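### The >90% power in Section 6.4 (30% vs 40% survival) is right for all ~1200 patients, but Section 6.3 estimates the selected ventilation rate in a ~360-patient hold-out, where that power is about 50%

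*Protocol*

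**What the plan says.** Section 2.1 lists as a secondary objective: "Determine if there is an alternative ventilation rate that is associated with improved 1) survival outcomes". The rate of interest is therefore one to be found in the data.

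Section 6.3, under Ventilation Rate and Survival, says how: "We will randomly divide our cohort into a derivation set (70%) and a validation set (30" percent). The derivation set is exploratory and is used to pick the target. Then "the validation set will be used to validate the rate selected and to provide an unbiased estimate of the effect" of reaching that target. A later sentence adds a logistic regression for any alternative target, without naming the data set.

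Section 6.4, under Secondary Analytic Objectives, takes off about 20% of subjects for unusable ventilation data and continues: "Given the remaining cohort (~1200 patients), we will have more than 90% power to detect an improvement in survival from 30% to 40" percent, if 40% to 60% of subjects are at target. It concludes: "Given the absolute change in survival associated with the ventilation target from our preliminary data was >20%, we are conservatively powered" for this aim. It adds: "In subgroups as small as 350, we will have >80% power to detect an improvement in survival probability from 30% to 45" percent. The 70/30 split does not appear in Section 6.4.

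**The concern.** The power statement and the analysis plan describe different samples. Section 6.4 powers a comparison in the whole cohort. Section 6.3 assigns validation and the unbiased estimate for the selected rate to 30% of it. Testing the selected rate in all ~1200 patients would reuse the 70% that chose it, which is the bias the hold-out is there to avoid.

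A reader of Section 6.4 would expect a 10-point difference to be estimated with the precision of about 1200 patients. If the validation result is then inconclusive, that reader could take it as evidence against an alternative rate, when the hold-out had only an even chance of detecting a difference of that size. The only power figure given for a sample near 360 is labelled for subgroups and uses a 15-point effect.

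**Working it through.** **Inputs from the protocol**
- "1500 index events will be available for analysis" (Section 6.4); about 20% lack usable ventilation data: 1500 × 0.80 = 1200.
- Validation share 30% (Section 6.3): 1200 × 0.30 = 360. Derivation set: 1200 × 0.70 = 840.
- Survival 30% off target and 40% at target, with a share *f* of 40% to 60% at target (Section 6.4).
- Two-sided alpha 0.05. Section 6.4 states this only for the blood pressure calculation; it is assumed here.

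**Formula.** Two-proportion test, pooled variance under the null, unadjusted. With n₁ = N(1 − f) off target, n₂ = Nf at target, and p̄ = (n₁p₁ + n₂p₂)/N:
- s₀ = √[p̄(1 − p̄)(1/n₁ + 1/n₂)]
- s₁ = √[p₁(1 − p₁)/n₁ + p₂(1 − p₂)/n₂]
- power = Φ[(p₂ − p₁ − 1.96 s₀)/s₁]
- 95% CI half-width = 1.96 s₁

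**Step 1: reproduce the protocol's figures**
- N = 1200, 30% vs 40%, f = 50%: n₁ = n₂ = 600, p̄ = 0.35, s₀ = 0.02754, s₁ = 0.02739. Then (0.10 − 1.96 × 0.02754)/0.02739 = 1.68, and power is 95.4%. With f = 40% or 60% it is 94.6%. The stated >90% is correct for 1200.
- N = 350, 30% vs 45%, f = 40/50/60%: 81.6/82.9/81.1%. The subgroup sentence also reproduces.

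**Step 2: same contrast in the validation set**
- N = 360, f = 50%: n₁ = n₂ = 180, s₀ = 0.05028, s₁ = 0.05000. Then (0.10 − 1.96 × 0.05028)/0.05000 = 0.029, and power is 51.2%.
- With f = 40% it is 50.1%, and with f = 60% it is 49.0%. A simulation of 200,000 runs gave 50.3/51.9/49.3%.

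**Step 3: other effects in the validation set (N = 360, 30% off target)**

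| Difference (points) | Power, f = 40 / 50 / 60% |
|---|---|
| 10 | 50.1 / 51.2 / 49.0% |
| 12 | 64.8 / 66.1 / 63.9% |
| 14 | 77.4 / 78.8 / 76.9% |
| 15 | 82.7 / 83.9 / 82.2% |
| 16 | 87.0 / 88.2 / 86.7% |
| 20 | 97.0 / 97.5 / 97.0% |

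The detectable difference is 14.5/14.2/14.6 points at 80% power and 16.8/16.5/16.9 points at 90%.

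**Step 4: precision for 30% vs 40%.** The 95% CI half-width is 10.1/9.8/9.9 points at N = 360, against 5.5/5.4/5.4 at N = 1200. Around an observed 10-point difference the hold-out interval is about 0 to 20 points.

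**Step 5: size needed.** For 90% power at 30% vs 40%, the set supplying the estimate would need about 950 to 995 patients.

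**Sensitivity.** A continuity correction lowers the N = 360 power to 44.5% to 46.7%. A one-sided 0.05 test raises it only to 62% to 64%. Clustering and covariate adjustment are not included.

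**The case against.** No figure in Section 6.4 is miscalculated. Both survival power statements reproduce, and the case is a mismatch between two sections. That is so, and the point claims no more.

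The later logistic regression in Section 6.3 names no data set, so it might use all ~1200 patients. The plan does not exclude this. But for a rate chosen in 840 of those patients, the result would not be the unbiased estimate that Section 6.3 assigns to the validation set.

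The word target in Section 6.4 could mean the known 20–30 bpm range. For a target fixed in advance no hold-out is needed, and >90% stands. However, the objective in Section 2.1 is an alternative rate, and Section 6.4 does not say that its figure is for something else. Labelling the figure settles this under either reading.

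Section 6.3 gives the hold-out an estimation role and promises no power there. This is fair, and the interval width is the more direct measure. It too is nearly twice what 1200 patients would give.

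The claim of conservative powering is tied to a preliminary effect above 20 points, and for 20 points the hold-out has about 97%. This stands. Yet the primary-objective part of Section 6.4 says "Understanding that it is likely that the magnitude of the effect will be smaller in a multicenter study" and plans on 12 to 16 points, a range over which the hold-out has 64% to 88%. That range belongs to survival with favorable neurologic outcome under the guideline target, so applying it here is an assumption.

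**Conclusion.** The concern holds. The >90% power for 30% versus 40% is correct for about 1200 patients, but it is not the power of the analysis that Section 6.3 designates for a rate selected from the data. In the ~360-patient validation set that power is about 50%, and the interval half-width is about 10 points instead of about 5.5.

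This rests on a two-sided 0.05 level, 30% survival off target, 40% to 60% at target (the protocol's range, carried over to a rate not yet chosen), and an unadjusted comparison without clustering. The >90% figure remains valid for a pre-specified target in the full cohort. The objective is secondary and observational; the power of the primary comparison is unaffected. The correction should be made, but it calls for no redesign.

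**What to change.** Restate the Ventilation Rate and Survival paragraph of Section 6.4 for the validation set. Suggested text:

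> Of about 1200 patients with usable ventilation data, about 360 will form the validation set. With 40–60% of them at target and 30% survival off target, the unadjusted 95% confidence interval for the difference in survival will be about ±10 percentage points. Power (two-sided 0.05) is about 50% for a 10-point difference, 64–66% for 12, 80% for about 14.5, 90% for about 17 and 97% for 20.

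Keep the existing >90% figure, but label it as applying only to a pre-specified target tested in the full cohort. If the 12-to-16-point range is used as a benchmark, say that it comes from the primary outcome. It would also help to name the data set for the later logistic regression in Section 6.3.

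The cost is two or three sentences in Section 6.4. The analysis method, the split and the number of patients stay as they are.
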